3.1. Study subjects

60 subjects with carpal tunnel syndrome will be randomized to 3 intervention groups as described above with stratification for age and gender. Subjects will be both male and female, ages 18-75. Subjects will be recruited from OHSU's EMG lab and neuromuscular clinic.

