4.4. Stratified Randomization

Subjects will be randomized to the 3 intervention groups, using a specially-designed computer program which will enable stratified randomization based on 2x2 categories where one category is gender (M/F) and the other is projected median age split of 56, based on age of enrolled pilots and clinic patients with carpal tunnel syndrome (18-56/57-75).

Gender and age have confounding effect on proper estimation of NCS and QST as they vary by age and sex. Specifically, men tend to have faster nerve conduction velocities (NCV) and larger nerves than women and with age NCV declines and sensory thresholds, measured by QST tend to rise (38, 49, 55, 56). Randomization will be performed by study acupuncturist, and all outcome assessors will be blinded to it.

The randomization program is also designed to offer random order of acupuncture intervention location (median vs ulnar nerves), with a built-in ability to assign 50% of subjects within a group to median nerve first and the other 50% - to ulnar nerve first.

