9. STATISTICAL CONSIDERATIONS

9.1. Sample Size Calculation

A mechanistic study of acupuncture, which examines its local, nerve-specific effects using Quantitative Sensory Testing (QST) and Nerve Conduction Studies (NCS) as outcome measures has not been attempted before. Therefore, we estimated acupuncture's effects based on larger studies drawn from the literature. Changes in acupuncture-associated sensation were derived from Lang et al (42) - an evaluation of manual and electroacupuncture- induced analgesia in the legs, using 24 healthy subjects, 12 men and 12 women, in a cross-over design. Effect sizes in Median nerve conduction velocity (NCV) were calculated as clinically relevant changes from the mean NCV reported by Kimura et. al (52) and Di Guglielmo et. al (53). Both studies were NCS characterizations specifically in CTS with 105 and 198 patients respectively and publicized in the AAEM summary statement on electrodiagnostic parameters in CTS (54).

QST testing from the Lang et al (42) acupuncture intervention was observed to be a significant predictor of Cold Detection Threshold (CDT), with a 0.2°C change ($-3.6 \pm 0.9^{\circ}\text{C}$ to $-3.4 \pm 0.4^{\circ}\text{C}$) seen in the low-frequency-acupuncture treated legs. As this study was conducted in healthy subjects, we expect to see a greater effect of acupuncture on patients with neuropathy, especially as the acupuncture will be administered locally, with greater potential to affect the underlying nerve. Sample size estimation assumed the variance of the change in QST outcomes due to local acupuncture delivery over the Median and Ulnar nerves will be comparable to the variance in QST observed by Lang after acupuncture in healthy nerves ($\sigma^2_{\text{CDT}} = 0.696 (^{\circ}\text{C})^2$). Under these assumptions, a minimum QST change of 0.35°C , considered reasonable as an on-treatment effect

size in CDT, would be observed as statistically significant at a significance level of $\alpha=0.05$ with 80% power with 20 subjects per arm.

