9.2. Stratified Randomization – See section 4.4

9.3. Outcome Measures and Statistical Hypotheses, as outlined in the Specific Aims

Specific Aim 1: Characterize the effects of acupuncture on QST (cold and vibration sensation thresholds) and nerve conduction parameters in the Median and Ulnar nerves.

Hypothesis: Acupuncture will cause decrease in cold and vibration detection thresholds (improve sensation) in the underlying nerve sensory distribution only. Acupuncture will cause NCS changes, characteristic of improved nerve function.

The outcomes generated in this aim will be the baseline and post-acupuncture values of CDT and VDT from Week 1 and Week 2, as well as baseline and post-acupuncture nerve conduction study data from both weeks, consisting of: distal motor/sensory latencies, CMAP and SNAP amplitudes, CMAP area and duration, nerve conduction velocities.

Specific Aim 2: Compare the effects of acupuncture on a diseased nerve (Median) to those of a healthy nerve (Ulnar), using QST (cold and vibration sensation thresholds) and NCS parameters.

Hypothesis: There will be greater change in cold and vibration detection thresholds and NCS parameters in the median nerve compared to the ulnar, due to the lower functional baseline of the median nerve.

The outcomes generated in this aim consist of statistical comparison of acupuncture-induced CDT, VDT and NCS changes in the Median nerve to those in the Ulnar nerve. The Post- minus Pre-acupuncture differences will be compared for the Median and Ulnar nerves in pooled data from all 3 groups, using independent sample t-testing.

Specific Aim 3: Compare the effects of manual acupuncture to those of low-frequency and high-frequency electroacupuncture.

Hypothesis: High-frequency electroacupuncture will have greater effect on NCS, QST followed by low-frequency electroacupuncture and manual acupuncture, in accordance to traditional practices. Acupuncture-induced changes in CDT, DVT and NCS parameters will be compared among the 3 groups (Post- minus Pre- changes), using ANOVA.

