9.4. Statistical Analysis Plan

Primary statistical analysis for all 3 Specific Aims will use linear mixed-effect models to evaluate the effects of treatment group and intervened nerve location on the outcome measures described above. A mixed-model design will be used to create an intention-to-treat framework

and allow for any missing data. Principal assessment will be on the change in outcomes resulting from acupuncture intervention, calculated as the difference in outcomes before and after treatment. These outcomes will include CDT and VDT, distal motor/sensory latencies, CMAP and SNAP amplitudes, CMAP area and duration, nerve conduction velocities (Specific Aim 1). Acupuncture characterization will be carried out first in the Median and Ulnar nerves of the arm (Specific Aims 1, 2). In both Median and Ulnar nerve interventions, group will be a three level factor based on the type of acupuncture - MA, LF-EA and HF-EA (Specific Aim 3).

Specific Aims 1 and 2:

As a principal independent variable, location of the intervention will be a four-level factor encompassing the possible combinations of treated and evaluated nerves. For Specific Aims 1 and 2, these levels will be: MM – Median treated and tested, MU – Median treated and Ulnar tested, UM – Ulnar treated and Median tested, and UU – Ulnar treated and tested. A time variable (Week 1, Week 2) will also be included to test for any effects due to order of the treated nerves. Additional covariates known to be associated with QST and NCS outcomes such as age and gender will be corrected for as well. Secondary analysis will include treatment evaluations of outcomes within each location of intervention and additional contrasts between the four time points (pre and post treatment for both Week 1 and Week 2). Persistence of the acupuncture effects will specifically be assessed by comparing changes in outcomes after the first treatment but before the second session.

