Specific Aim 3: We will revise the linear mixed model and focus on the MM factor from Specific Aims 1 and 2 (Median nerve treated and tested). In this revised model we will incorporate acupuncture modality as a 3-factor covariate (MA, LF-EA, HF-EA). Incorporating both the 4-factor sets of nerve intervention/assessment combinations and the 3-factor acupuncture modality would create a very complex model with over 15 variables. As described in the washout analysis, this will lead to overfitting of the model and cause it to be underpowered at 60 subjects. We could run a similar revised mixed liner model analysis substituting UU, UM or MU for MM, although this would be beyond the scope of Specific Aim 3.

Because of the exploratory nature of our analyses, no adjustment for multiple testing will be undertaken. Raw *P* values 0.05 will be regarded as statistically significant. Regardless, the multiple assessments inherent in the exploratory analysis will be discussed in future publications. Statistical analysis will be performed using SAS 9.1 (SAS Institute, Cary, NC).

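### The Aim 3 modality comparison has no single stated model, and the age, gender and order factors used in the randomisation are not carried into it

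*Combined protocol and SAP*

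**What the plan says.** **Randomisation.** Section 3.1: "60 subjects with carpal tunnel syndrome will be randomized to 3 intervention groups as described above with stratification for age and gender". Section 4.4 defines the strata as gender by age (18-56 or 57-75) and describes a program "with a built-in ability to assign 50% of subjects within a group to median nerve first", with the other half treated ulnar first. The reason given for the strata is that nerve conduction (NCS) and sensory testing (QST) values differ by age and sex.

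**Aims 1 and 2.** Under that heading in section 9.4, the model has a four-level location factor and a Week 1/Week 2 term, and "Additional covariates known to be associated with QST and NCS outcomes such as age and gender will be corrected for as well".

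**Aim 3.** Section 9.3 says that the changes "will be compared among the 3 groups (Post- minus Pre- changes), using ANOVA", with no covariate named. Section 9.4 opens by making linear mixed models primary for all three aims. For Aim 3 it says that the Aims 1 and 2 model will be revised and focused on MM: "In this revised model we will incorporate acupuncture modality as a 3-factor covariate (MA, LF-EA, HF-EA"). Age, gender and week are neither kept nor removed there. Section 9.4 also says that the dependent variable of every model is the change from baseline to post-acupuncture, and that no multiplicity adjustment is made: "Raw *P* values 0.05 will be regarded as statistically significant".

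**The concern.** Aim 3 is the comparison between the parallel arms, and section 9.1 itself describes the modality contrasts as between subjects. It is therefore where covariates related to the outcome can reduce error variance. Stratification removes most of the age and gender difference between arms, and balancing does the same for order. A model without these factors still counts their variance as residual error. The reported standard error is then larger than the real sampling variation, so intervals are too wide and the test rejects less often than its nominal level.

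Week matters for the same reason. MM is a Week 1 change for median-first subjects and a Week 2 change for ulnar-first subjects, so in MM-only data week and order are the same variable. Section 5.2 says that a single session may alter the parameters measured a week later.

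There is also a specification issue. With two descriptions of Aim 3 and no statement on covariates, the choice between an adjusted and an unadjusted result could be made after seeing the data, across many outcomes at an unadjusted 0.05.

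**Working it through.** **Inputs from the documents.** Alpha is 0.05 (taken as two-sided; the plan does not say), with 20 per arm. For cold detection threshold (CDT), section 9.1 uses "a minimum QST change of 0.35°C" and a variance of 0.696, so SD = √0.696 = 0.834 °C. For conduction velocity (NCV), it uses 3.7 m/s and SD 5.76 m/s. All models use change scores.

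**Assumption.** R² is the share of change-score variance explained jointly by age stratum, gender and order. The documents give no value, so a range is shown.

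**The plan's own figure.** Section 9.1 claims its detectable changes "with 80% power with 20 subjects per arm". These are within-arm changes, so n = (SD × (1.96 + 0.8416) / δ)².
- NCV: (5.76 × 2.8016 / 3.7)² = 19.02, so 20. This reproduces.
- CDT: (0.834 × 2.8016 / 0.35)² = 44.6, so 45. This does not reproduce, which is a separate matter.

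No power figure is given for the modality comparison. The same effect sizes are used below as differences between two modalities, for illustration only.

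**Pairwise contrast, 20 against 20.** The standard error reported without adjustment is S = SD × √(2/20): 5.76 × 0.3162 = 1.8215 m/s for NCV and 0.834 × 0.3162 = 0.2638 °C for CDT. With the factors balanced, the true standard error is T = S × √(1 − R²). Then:
- interval inflation without adjustment = S/T = 1/√(1 − R²)
- type I error without adjustment ≈ 2 × (1 − Φ(1.96 × S/T))
- power without adjustment ≈ Φ((δ − 1.96 S)/T)
- power with adjustment ≈ Φ(δ/T − 1.96)

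| R² | Interval inflation | Type I error, unadjusted | NCV power, unadjusted to adjusted | CDT power, unadjusted to adjusted |
|---|---|---|---|---|
| 0 | 1.00 | 5.0% | 52.8% to 52.8% | 26.3% to 26.3% |
| 0.10 | 1.05 | 3.9% | 53.0% to 57.2% | 25.2% to 28.7% |
| 0.20 | 1.12 | 2.8% | 53.2% to 62.2% | 23.9% to 31.7% |
| 0.30 | 1.20 | 1.9% | 53.4% to 68.0% | 22.5% to 35.4% |

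Worked line, NCV at R² = 0.20: T = 1.8215 × √0.8 = 1.6292. Unadjusted: (3.7 − 1.96 × 1.8215)/1.6292 = 0.080, so 53.2%. Adjusted: 3.7/1.6292 − 1.96 = 0.311, so 62.2%.

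**Simulation check.** The setting was 60 subjects, permuted blocks of 3 within gender-by-age strata, order balanced within arm, an assumed 65% women and 50% in the older stratum, and 8,000 runs per setting. It gave type I error, unadjusted against adjusted, of 0.044 and 0.045 at R² = 0, 0.039 and 0.052 at 0.10, and 0.028 and 0.048 at 0.20. Power for a 0.9 SD difference was 0.81 and 0.81, 0.81 and 0.84, and 0.82 and 0.88.

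A further simulation with permuted blocks in strata tested all three arms together at assumed means of 0, 0.275 and 0.55 °C. Type I error was 3.5% and 4.6% at R² = 0.10, and 2.7% and 4.9% at 0.20. Power was 40% and 46%, then 40% and 53%. When the factors are made exactly balanced, the unadjusted type I error at R² = 0.20 falls to 2.1%.

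**Cost in parameters.** Modality alone uses 3 parameters and leaves 60 − 3 = 57 residual degrees of freedom. Three added binary factors leave 54.

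**The case against.** The strongest reply is that section 9.4 governs. It makes mixed models primary for all three aims, and its Aim 3 model is a revision of one that already contained age, gender and week. Nothing says they are removed, so a natural reading keeps them. This stands: a reader might infer that the plan excludes the randomisation factors from Aim 3, but that is firm only for the section 9.3 ANOVA. For section 9.4 it is silence.

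A reader might also infer that the plan's overfitting remarks argue for dropping age and gender. They do not. One concerns time-dependent interactions in the wash-out analysis. The other concerns crossing four locations with three modalities, a model of over 15 variables.

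Second, the loss depends on R² for a change score. Section 4.4 supports age and gender as predictors of level, and differencing may remove much of that. This also stands, so the claim that power is lost cannot be made without the condition. The plan does give some reason to expect a relation. It predicts larger change where baseline function is lower, says that baseline varies with age and sex, and already corrects change-score models for both under Aims 1 and 2.

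Third, any error is conservative, in a pilot whose analyses are declared exploratory. That limits the harm but is no reason to leave the model unstated.

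Two further inferences go too far. Modality is not the only randomised factor, because nerve order is randomised too. Nor is adjustment useless for Aims 1 and 2: subjects who leave after Week 1 stay in the analysis, so those contrasts are not purely within subject.

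**Conclusion.** The point holds as a gap and an inconsistency in specification: sections 9.3 and 9.4 describe different Aim 3 analyses, and neither states that the randomisation factors are included. It does not hold as a demonstrated loss of power.

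The size is conditional on R². Nothing is lost at 0. At 0.10, unadjusted type I error is about 3.5-4% and about 3-6 points of power are lost. At 0.20, the figures are about 2-3% and 5-13 points. The ranges reflect different effect sizes and different degrees of balance. They assume complete data on 60 subjects and the section 9.1 standard deviations.

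Adjustment does not rescue Aim 3. Even at R² = 0.30, adjusted pairwise power at the illustrative differences is 35% for CDT and 68% for NCV. This is a free improvement: a better-defined analysis at almost no cost.

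**What to change.** In section 9.4, state one Aim 3 model for each outcome: MM change on modality, age stratum (18-56 or 57-75), gender, and the week in which the median nerve was treated (which is the order). Say that all terms are kept whatever their P values. Replace the plain ANOVA in section 9.3 with this model.

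MM-only data give one change score per subject per outcome, so this is an ANCOVA-type linear model. A subject random effect cannot be estimated, and the mixed-model label should be dropped for this aim.

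The cost is a few lines of wording and 3 of 57 residual degrees of freedom. The model has six parameters for 60 subjects, well short of the 15-variable model the plan wants to avoid. No change to randomisation, visits or data collection is needed.

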3.2. Study site

OHSU will be the only study site for this protocol

3.3. Experimental duration and follow-up

Study procedures will be carried out over 2 consecutive weeks (see **Figure 1**). As this is a mechanistic study involving immediate effects of acupuncture on a peripheral nerve, there will be no follow up period beyond Week 2. This study employs 3 commonly practiced, well established interventions, which are considered low-risk: nerve conduction studies (NCS), quantitative sensory testing (QST) and acupuncture to the forearm. Subjects will be given all necessary follow-up contact information in case of unanticipated adverse events, as described in Section 7 (Safety Assessments).

3.4. Blinding

As this is a mechanistic study comparing acupuncture to acupuncture intervention, it is impossible to blind subjects in the conventional sense. Depending on a subject's knowledge of anatomy and acupuncture, however, a subject may or may not be aware as to which nerve is targeted for intervention on each week.

All QST assessments will be performed in blinded fashion and the investigators assessing the outcome measures will not be delivering the intervention (acupuncture). QST assessments will be performed by a blinded investigator ([name]), who will be seated behind a screen with the subject's arm, needles and QST probes not visible. The PI will not be involved in QST measurements. Additionally, the PI will be blinded to the acupuncture intervention, which will be delivered by a licensed acupuncturist ([name] or [name]).

Week 1 QST and NCS baseline will be assessed in non-blinded fashion, prior to randomization. Following these initial measurements, the PI will screen the subject for Secondary Exclusion criteria. Once the subject is determined eligible, the PI will leave the room. PI will be blinded to randomization (MA, LF-EA or HF-EA) and treatment assignment (median or ulnar nerve). Randomization will be performed by the study acupuncturist and the other investigators will be blinded to it.

The PI will return to the room once the acupuncture intervention has been completed, the post-acupuncture QST measurements obtained and acupuncture needles removed, in order to perform the post-acupuncture NCS and remain blinded to the intervention.

4. SELECTION AND ENROLLMENT OF PARTICIPANTS

4.1. Inclusion Criteria

Participants must meet all of the following inclusion criteria to participate in the study:

- Age 18-75
- Both male and female subjects
- Presence of mild-moderate sensorimotor or sensory median neuropathy, established by pre-existing NCS/EMG study AND
- **Baseline NCS study within the past 2 years**, consistent with mild-moderate median entrapment neuropathy (CTS) defined as meeting any of the 3 conditions below (33, 34):
 1. Prolonged distal Median sensory AND/OR motor latency
 2. Reduced Median sensory nerve action potentials (SNAP) amplitude by no more than 50%
 3. Amplitude of the compound muscle action potential (CMAP) recorded from APB > 50% of normal
- Presence of neuropathy symptoms consistent with CTS for at least 3 months (36)

4.2. Exclusion Criteria

Patients will be excluded on initial screening in the EMG lab or the Neuromuscular clinic at OHSU based on the following Exclusion Criteria:

Conditions in which acupuncture/electroacupuncture may be contraindicated:

- Coagulopathy/ Current anti-coagulation treatment
- Epilepsy
- History of CAD or pacemaker insertion
- Pregnancy
- Presence of any skin condition in the arm, such as dermatitis, bruises, weeping skin, skin lesions, infected skin, or necrotic skin.

Conditions in which QST testing may be contraindicated:

- Significant cognitive impairment such as diagnosis of Alzheimer’s disease or Mental Retardation or any other condition interfering with alertness, attention and ability to participate in QST
- Hospitalization for anxiety or depression in the past 3 months
- Current psychiatric diagnoses (other than anxiety or depression)
- Illicit drug use in the past month
- Current EtOH abuse (> 2 drinks/day)
- History of significant neurological disease which may affect sensation, e.g., strokes, Multiple Sclerosis, or spinal cord disorder
- Change in neuropathy medications within the past 2 months
- Change in opioid, benzodiazepines, SSRIs or other sedating medications in the past 2 months

Conditions, which predispose to generalized neuropathy

- Abnormal thyroid function tests (by history)
- Past chemotherapy treatment

Other Contraindications:

- History of wrist or elbow fracture, past arm trauma, loss of fingers, scarring
- History of carpal tunnel release surgery or any other surgery on the arm or shoulder
- History of arthritis
- Use of any investigational drugs within the previous six months

Exclusion Criteria based on NCS within the past 2 years:

- Presence of isolated motor Median neuropathy (absence of sensory neuropathy on NCS or absence of sensory symptoms)
- Severe neuropathy symptoms leading to inability to tolerate acupuncture or QST
- **Presence of Severe Carpal Tunnel Syndrome, defined as:**
 1. Absent sensory nerve action potential recorded from the second or fifth digit.
 2. The amplitude of the compound muscle action potential recorded from the APB or ADM is less than 50% of normal (< 2.5 mv)
- Presence of Ulnar neuropathy
- Presence of Martin-Gruber anastomosis

Secondary Exclusion Criteria after WEEK 1 Baseline QST and NCS measurements (See Figure 1):

- Failure to comply with QST due to inattentiveness, etc
- Hyperalgesia on QST
- Hypoalgesia on QST
- Inability to confirm diagnosis of mild-moderate CTS (normal NCS)
- Inability to tolerate NCS/QST
- Presence Severe CTS

- Pure Motor Median Neuropathy
- Ulnar Neuropathy

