4.3. Study Enrollment Procedures

Potential participants will be identified through screening OHSU's EMG lab and neuromuscular clinic patient schedules. Basic eligibility screening will be conducted using OHSU's electronic medical record database (EPIC). Patients, who pass this medical record screening will be approached by the PI. If a patient is interested, the PI will explain the objectives, risks and benefits of the study. At this point if a patient agrees to screening, the PI will proceed with an evaluation based on medical history, habits and recent (within last 2 years) EMG/NCS. The screening results will be documented using the *Subject Screening Form* (Appendix A). If a potential subject is determined to be eligible, the PI will answer all his/her questions, inform the subject that he/she may withdraw consent at any point and obtain informed consent for the study. This will involve presenting the subject with a *Lay Language Protocol Summary* and an *OHSU Consent-and-Authorization form* (as required by OHSU IRB) is also included in Appendix A.

Following enrollment, subjects will come to the lab for initial screening, consisting of QST and NCS. Following this testing, if they pass the Secondary Exclusion Criteria, subjects will be randomized to MA, LF-EA and HF-EA, using a computer-generated stratified randomization based on age and gender.

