5.2. Experimental Procedure Timeline (Figure 1)

During Week 1, enrolled and consented subjects will come to the lab for Week 1 Baseline QST and NCS testing as outlined above. During this baseline testing subjects will be introduced to the QST equipment and will undergo assessment of baseline cold detection threshold (CDT) and vibration detection threshold (VDT), as well as baseline NCS as outlined above. This would take approximately 1.5 hours and both procedures are non-invasive.

Following assessment of Baseline QST and NCS, subjects will be screened for Secondary Exclusion criteria, which relate to their CTS diagnosis and ability to tolerate NCS and QST (**Figure 1**). Subjects who do not pass the Secondary Exclusion Criteria will exit the study, with proper documentation of why they were ineligible.

Those who pass the Secondary Exclusion Criteria will be randomized to MA, LF-EA and HF-EA, as well as undergo random treatment assignment of median (PC3, PC5) or ulnar (HT3, HT4) nerve. Following randomization a subject will undergo acupuncture for 20 minutes involving 2 needles as outlined in detail above.

Following acupuncture, Week 1 Post-acupuncture QST (CDT and VDT) and NCS will be obtained in a manner analogous to the Week 1 Baseline QST and NCS testing outlined above. QST will be obtained first, with the needles retained in position, followed by needle removal and conduction of NCS. This will conclude Week 1. Total estimated time of Week 1 procedures is 4-4.5 hours. Subjects will be provided with water, bathroom break/other breaks as needed and a healthy snack.

Week 2 procedures will occur exactly one week after Week 1, as close to the same time of day as possible. Week 2 will start with Week 2 Baseline QST and NCS testing, following the same methodology as the Week 1 Baseline QST and NCS outlined above, although subjects will not be screened for inclusion/exclusion criteria at Week 2. A second baseline is necessary because in our experience even a single intervention to PC3, PC5 or HT3, HT4 may alter NCS and QST parameters of the median and ulnar nerves, respectively.

Once Week 2 Baseline QST and NCS testing is obtained, acupuncture will be delivered to the nerve not treated during Week 1. For example, if a given subject is randomized to LF-EA and randomly assigned to ulnar nerve acupuncture in Week 1, the same subject will be administered LF-EA to the median nerve in Week 2, following Week 2 Baseline QST and NCS (Figure 1).

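### Anticoagulation, pregnancy and arm skin conditions are checked only at enrolment; a short check before each needling session would be a minor, cheap safety improvement

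*Combined protocol and SAP*

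**What the plan says.** Section 4.2 lists five conditions in which acupuncture or electroacupuncture may be contraindicated: coagulopathy or current anticoagulation, epilepsy, coronary disease or a pacemaker, pregnancy, and arm skin disease. The last is worded broadly: "Presence of any skin condition in the arm, such as dermatitis, bruises, weeping skin, skin lesions, infected skin, or necrotic skin". The time of application is given once: "Patients will be excluded on initial screening in the EMG lab or the Neuromuscular clinic at OHSU based on the following Exclusion Criteria".

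The next eligibility step is the Week 1 laboratory visit. Section 4.3 describes it this way: "Following enrollment, subjects will come to the lab for initial screening, consisting of QST and NCS". Section 5.2 gives its scope: "subjects will be screened for Secondary Exclusion criteria, which relate to their CTS diagnosis and ability to tolerate NCS and QST". Treatment then follows: "Following randomization a subject will undergo acupuncture for 20 minutes involving 2 needles as outlined in detail above".

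For the second visit, section 5.2 fixes the date ("Week 2 procedures will occur exactly one week after Week 1, as close to the same time of day as possible"), repeats the baseline QST and NCS "although subjects will not be screened for inclusion/exclusion criteria at Week 2", and continues: "Once Week 2 Baseline QST and NCS testing is obtained, acupuncture will be delivered to the nerve not treated during Week 1".

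The section 6 schedule ticks the investigator's study screening and the Screening Form in the screening column only. Acupuncture is ticked at Week 1 and Week 2.

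**The concern.** A contraindication that can change protects the subject only if it is current when the needle goes in. Epilepsy and a history of coronary disease or a pacemaker are history items and are not at issue. Skin condition, anticoagulant use and pregnancy can all change between enrolment and a session. If the schedule is followed as written, a subject who has started an anticoagulant or become pregnant since screening could be needled without anyone having been required to ask. The first session can also produce a listed exclusion: section 7 names minor bleeding and ecchymoses as a risk, and 4.2 counts bruises as a skin condition. What is at stake is subject safety on a small scale, not the validity of the comparisons.

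**Working it through.** The plan states no figure on this point, so the check sets the relevant sections side by side.

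| Step | What is checked | Skin, anticoagulant, pregnancy? |
|---|---|---|
| Enrolment screening (4.2, 4.3, Subject Screening Form) | History, medication, recent NCS | All three |
| Week 1 laboratory screening (4.2 Secondary list, 4.3, 5.2) | QST compliance and result, CTS status, tolerance | None |
| Week 1, randomization to needling (5.1.3, 5.2) | No check stated | None |
| Week 2, baseline to needling (5.2) | Repeat QST and NCS | None |
| Data Form and 10.1 | Acupuncturist enters points and modality at the end of the session | None |
| Adverse events (section 6 row, 7.1, 7.3) | Any adverse event, whatever its cause; exit for unanticipated events | Partly; not tied to a time before needling |

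**Counts**
- Acupuncture contraindications in 4.2: 5, of which 3 can change.
- Secondary Exclusion items: failure to comply with QST, hyperalgesia, hypoalgesia, CTS not confirmed, intolerance of NCS or QST, severe CTS, pure motor median neuropathy, ulnar neuropathy. That is 8, and 0 of the 3 changeable conditions are among them.
- The 4.2 screening is ticked in 1 of 3 schedule columns and at 0 of 2 needling visits.
- Planned sessions: 60 subjects × 2 = 120, none preceded by a written same-visit check of the three conditions.

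**Time windows**
- Screening to Week 1: no maximum is stated. Section 4.5 recruits immediately after the clinical NCS/EMG and expects 2 to 4 enrolments a month against capacity for 4 to 5. This suggests no backlog, but it does not bound any one subject's wait.
- Week 1 to Week 2: 7 days.

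**What existing cover leaves open**
- Visible skin problems are mostly covered. Baseline NCS and the acupuncturist put the arm in view, and 7.3 exits subjects for needling-site infection or moderate to severe bruising.
- A new anticoagulant or a pregnancy cannot be seen. Subjects are invited under 7.2 to report concerns, but no one has to put the question.
- The documents give no incidence for either, so the number of subjects affected cannot be calculated.

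**The case against.** The case for leaving the plan alone is substantial. Section 4.2 says only that acupuncture may be contraindicated. Section 7 describes the bleeding harm as minor and the needle as 30G and solid; 5.1.3 gives a depth of 3 to 5 mm. Section 7 also names anti-platelet users as being at higher risk, yet 4.2 does not exclude them, so the protocol already accepts some bleeding risk. Pregnancy can concern only a minority: men are enrolled and the projected median age is 56. A new pregnancy or anticoagulant within seven days is unlikely, and an illness that led to anticoagulation would itself be an adverse event under 7.1. Week 2 needles the other nerve's points, so bruising from session 1 need not lie at the new sites. All of this stands, and it limits the weight of the point. It does not supply the missing question before needling.

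Three stronger readings are tempting, and the documents do not support them.
- A reader might infer that 5.2 forbids any safety check at Week 2. The clause sits in a sentence about repeating the baseline QST and NCS, so it most naturally refers to those entry criteria. It is loosely worded, not a ban.
- A reader might infer a long, uncontrolled gap before session 1. No limit is written, but the recruitment figures in 4.5 point to a short wait.
- A reader might infer that subjects are unprotected. The adverse-event rules, the contact number and the acupuncturist's own view of the arm are real cover, and the exit reasons in section 8 are not worded as exhaustive.

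**Conclusion.** The gap is real but minor. Three conditions that the protocol itself treats as possible contraindications can change after the only point at which they are checked. For two of them, new anticoagulation and pregnancy, nobody is required to ask before needling. Few subjects would be affected and no rate can be given. Outcomes, power and the significance level are untouched, and the design is not undermined.

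The conclusion rests on the text available. Figure 1 and the consent pages are not shown, and the data and safety monitoring plan appears only in summary. Any of these could hold a related instruction, and the acupuncturist may ask as a matter of routine. The point concerns what is written, not what is done.

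**What to change.** 1. In 5.2, limit the Week 2 clause to the CTS-severity and QST/NCS entry criteria.
2. Add one row to section 6, at Week 1 before randomization and at Week 2 before needling. The acupuncturist asks about new anticoagulants and pregnancy and looks at the arm. At Week 1, re-apply the arm-wide skin criterion of 4.2. At Week 2, apply it only to the planned needling sites, so that minor bruising elsewhere from session 1 does not bar session 2.
3. Record the Week 1 result before the randomization program is opened. Under 3.4 the acupuncturist also randomizes, and this order keeps the assignment from influencing eligibility.
4. Add a positive check to the section 8 reasons, keep Week 1 data under 5.3, and report withheld sessions with reasons by group. Withhold session 2 rather than delay it, because 5.2 fixes the interval.

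**Cost.** One clause, one row, one line, and about a minute per visit. A Week 1 failure occurs before randomization and falls within the allowance in 9.1: about 75 enrolled for 60 completers, 75 − 60 = 15. A withheld Week 2 session costs more. That subject's within-subject contrast of median treated and tested (MM) with ulnar treated and tested (UU) is lost, although the mixed model still uses the Week 1 data. If the contrast within one modality rested on complete pairs alone, losing 1 of 20 would widen its standard error by √(20/19) = 1.026, about 2.6%, and losing 2 of 20 by √(20/18) = 1.054, about 5.4%, with the variance unchanged. Such losses may be related to session 1, which is why they should be reported by group.
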